3.4.2 Adenovirus Safety

Adenoviral vectors have been used extensively to deliver a variety of gene products to human subjects, including cancer patients. Although adenoviral vectors are immunogenic, and virtually all recipients have pre-existing humoral immunity to adenoviruses, they are generally considered to be a safe, well-tolerated method of gene delivery that results in minimal side effects in subjects.

In a Phase I/II clinical trial in prostate cancer using direct intraprostatic injection of a replication-defective adenovirus vector encoding bacterial nitroreductase (dose levels 5×10^{10} - 1×10^{12} virus particles), the vector was well tolerated, with minimal side effects, and had a short half-life in the circulation.²⁶ Numerous studies have utilized adenoviral vectors to deliver the p53 gene via the IT route. Oral leukoplakia subjects who were given multiple intraepithelial injections of recombinant adenovirus (rAd)-p53 (1×10^8 virus particles/cm²) did not demonstrate signs of dose-limiting toxicity (DLT), and administration of the (rAd)-p53 was well tolerated.²⁷ No DLT was observed in chemoradiation-resistant advanced esophageal carcinoma subjects receiving IT injections of adenovirus containing p53 (10×10^{11} particles to 25×10^{11} particles).²⁸ Adverse events attributed to Ad.5CMV-p53 treatment were generally mild to moderate, with the most common AEs being Grade 1 or 2 fever (100 % of subjects) and local pain (30% of subjects.) Three subjects displayed hyperglycemia that was attributed to nutrition, 2 subjects showed hypocalcemia, and 1 subject each experienced partial thromboplastin time (PTT) elongation or an increase in serum amylase or creatinine. No other significant laboratory abnormalities were detected on follow-up evaluations.²⁸

[figure not shown]
An adenoviral vector encoding hIL-12 has been studied using IT injection in subjects with advanced digestive malignancies, at doses up to 3×10^{12} vp, and was well tolerated. Common AEs were similar to symptoms observed with gene delivery by other adenoviral vectors, including transient, mild to moderate fever, malaise, sweating, and lymphopenia.²⁹

[figure not shown]
3.4.3 Safety of Intratumoral Injection of IL-12 genes

In comparison with administration of recombinant IL-12 protein, injection of plasmids or adenovirus containing hIL-12 genes to cancer subjects has proven to limit or abrogate the toxic effects of hIL-12, thus providing an effective way to provide this potent immunomodulatory cytokine. In Phase I and II clinical trials where IL-12 was delivered locally, increased systemic IL-12 serum levels post-baseline were not observed.³⁰⁻³²

Numerous studies have shown gene delivery of IL-12 to be well tolerated. In a Phase I dose-escalation trial using electroporation to administer plasmid DNA-encoding hIL-12 into metastatic melanoma, minimal systemic toxicity and no IL-12-related AEs were observed in subjects treated at several dose levels. Similarly, IT injection of a plasmid DNA-encoding human IL-12 (2 to 20 mg of total DNA) in subjects with melanoma was also well tolerated.³⁴ Limited elevations in serum cytokines were observed after treatment. Intra-peritoneal (IP) injection of hIL-12 plasmid DNA formulated in polyethyleneglycol-polyethyleneimine-cholesterol given to women with chemotherapy-resistant recurrent ovarian cancer also was found to be generally safe and well tolerated. Low-grade fever and abdominal pain were the most common side effects.³⁸ Plasmid DNA was not detected in the subjects' serum samples, and treatment-related increases in IFN- γ levels were observed only in pleural fluid but not in

serum. Similar findings have been obtained with IT injection of adenoviral vectors encoding hIL-12 at doses ranging from 2.5×10^{10} to 3×10^{12} vp, to subjects with advanced pancreatic, colorectal, or primary liver malignancies.²⁹ Treatment was well tolerated and DLT was not reached. AEs were transient, with fever, malaise, sweating, and lymphopenia being the most commonly observed. No cumulative toxicity was observed. All AEs were deemed to be related to injection of the virus and not to transgene expression.

[figure not shown]

3.5 Rationale for Study Design and Dose Selection

The objectives of this Phase II clinical trial are to assess the safety and tolerability, PFS rate at 16 weeks, ORR, and immunological and biological effects of IT injections of INXN-2001 + INXN-1001 as monotherapy or in combination with palifosfamide. To provide an opportunity to monitor the safety of Ad-RTS-hIL-12 monotherapy and Ad-RTS-hIL-12 + palifosfamide (combination therapy) in subjects with breast cancer, a safety run-in will occur, with evaluation following one cycle of study drug.

The study will commence with Ad-RTS-hIL-12 monotherapy using a 140-mg dose of INXN-1001 administered daily Days 1-7 in 6 subjects (21-day cycle). Following a safety assessment, combination therapy of Ad-RTS-hIL-12 + palifosfamide (120 mg/m², Days 1, 2, 3 of a 21-day cycle, n=3) will commence. Safety in Part 1 of the study will determine commencement of randomization for Part 2.

During the conduct of this study, in addition to monitoring of safety and therapeutic efficacy, peripheral blood samples will be studied for indications of immunological and biological effects including analyses of breast cancer-associated cytokines/biomarkers. The combined clinical and laboratory data will be studied to assess for activity, and will be used in decision making for expansion of treatment arms.

The population for this study was selected as those subjects with recurrent or metastatic breast cancer (which is rarely curable with standard therapy) and accessible lesions, who are therefore considered to be appropriate candidates for clinical trials exploring new forms of treatment. Because breast cancers may be responsive to immunotherapeutic approaches (see [Section 4.1 Disease Background](#)), this subject population may potentially benefit from investigational therapy with Ad-RTS-hIL-12 alone or in combination with palifosfamide.

4. STUDY OBJECTIVES AND DESIGN

4.1 Objectives

The primary objectives are to:

- Assess the safety and tolerability of INXN-1001 + INXN-2001 (Ad-RTS-hIL-12) as monotherapy and in combination with palifosfamide in subjects with recurrent and/or metastatic adenocarcinoma of the breast and accessible lesions (ie, in the opinion of the investigator is/are palpable and/or injectable), which are not amenable to surgical resection or radiation with curative intent
- Assess the efficacy of repeated cycles of IT injections of INXN-2001 (Ad-RTS-hIL-12) with INXN-1001 (oral activator ligand) as monotherapy or in combination with palifosfamide as measured by the 16-week progression-free survival (PFS) rate, defined as the proportion of subjects who survive progression-free at week 16 in the study population

The secondary objectives are to:

- Estimate PFS by modified Response Evaluation Criteria in Solid Tumors (mRECIST) v1.1
- Assess ORR by mRECIST v1.1
- Assess duration of response
- Assess clinical benefit rate (CBR = proportion of subjects with complete response [CR], partial response [PR], or stable disease [SD]) by mRECIST v1.1
- Evaluate pharmacodynamic tumor markers (eg, breast cancer-associated biomarkers such as MUC-1)
- Assess the PK of INXN-1001 in subjects with recurrent and/or metastatic adenocarcinoma of the breast

4.1.1 Study Design and Treatment Arm Expansion Procedure

4.1.1.1 Overall Study Design

This is a randomized, open-label, Phase II study of Ad-RTS-hIL-12 monotherapy or Ad-RTS-hIL-12 in combination with palifosfamide in subjects with recurrent/metastatic breast cancer with accessible lesions.

Two treatment arms will be assessed for safety, followed by random assignment to Ad-RTS-hIL-12 monotherapy or combination therapy. Each subject will be treated for up to 6 treatment cycles, with each cycle being 21 days in duration.

Safety and tolerability will be assessed by the incidence and severity of AEs as determined by National Cancer Institute (NCI) Common Terminology Criteria for Adverse Events (CTCAE) v4.03. A SRC comprised of the Medical Monitor, enrolling Principal Investigators (PIs), and Sponsor representatives, will be convened to review safety information and to decide upon further subject enrollment.

The antitumor activity of study treatment will be assessed according to mRECIST v1.1 guidelines.³¹ ([Appendix 4](#))

4.1.2 Treatment Parameters and Duration

Subjects will receive IT injections of INXN-2001 [REDACTED] [REDACTED] [REDACTED] on Day 1 of each cycle, will also receive oral doses of INXN-1001 (140 mg daily) for 7 days. Subjects enrolled in Arm C combination therapy will also receive palifosfamide (120 mg/m²/day) by IV infusion over approximately 30 minutes on Days 1, 2, 3 of each cycle.

All subjects may receive up to 6 cycles of study treatment. Subjects receiving Ad-RTS-hIL-12 with disease progression (per mRECIST v1.1 criteria) may still complete the 6 treatment cycles, because tumor nodules may enlarge due to the anticipated induction of an inflammatory response, unless the progression is clinically significant in the opinion of the investigator (see [Appendix 4](#)). Furthermore, in studies with a diversity of immunotherapies in different cancer types, objective responses have been shown to occur after an increase in tumor burden characterized as progressive disease (PD) by World Health Organization or RECIST criteria.

4.1.3 Safety Review Committee (SRC)

An SRC comprised of the Medical Monitor, enrolling PIs, and Sponsor representatives will hold periodic teleconferences to evaluate the safety and treatment status of all subjects available during the Safety Run-in (Part 1) at several stages:

- after 6 subjects Arm A have completed the first cycle,
- after 3 subjects in Arm C have completed the first cycle,
- at any other time as needed following random assignment in Part 2.

The safety run-in of Arm C (n=3) will occur with a 1-week interval between dosing of subjects and an SRC will convene after all subjects have received 1 cycle of therapy. The SRC has the authority to recommend dose or regimen modifications for safety concerns.

A written summary documenting the results and recommendations of each review will be provided to the investigator(s) and maintained on file with the Sponsor. Additional sub-investigators and personnel may participate in reviews, as appropriate.

Following a treatment arm review, the SRC may recommend proceeding with enrolling additional subjects in the current treatment arm or not enrolling any additional subjects.

While the SRC is expected to reach a consensus opinion regarding any premature discontinuation or significant modification of the study, the Sponsor may independently stop the study at any time.

4.1.4 Enrollment Procedure

During **Part 1**, 6 eligible subjects will enroll into Arm A, followed by 3 subjects in Arm C.

During **Part 2**, eligible subjects will be randomly assigned by the Sponsor or its representative:

- Subjects will be adaptively randomized in a 1:1 ratio to receive Ad-RTS-hIL-12 monotherapy (Arm A) or combination therapy (Arm C) according to the current status of the treatment arms and whether or not a subject has consented to the “Additional Immunologic Assessments” until the desired number of subjects is fully enrolled in each study arm.

4.1.5 Treatment Arm Expansion Procedure

Should a subject discontinue study treatment before receiving 6 cycles for reasons other than progression, another subject may be added to the treatment arm to allow for full analysis. Response evaluation and criteria for futility are described in [Section 9 Statistical Methods](#).

Subject enrollment and expansion of treatment Arms A and C will proceed according to a standard Simon 2-stage design ([Table 1](#)). An alternate dose level of palifosfamide and/or INXN-1001 may be explored after review of all available safety and activity data, and will be communicated by an administrative letter and enacted upon issuance.

Table 1 Study Design (see Protocol Synopsis)

Part	Treatment Arm	Intervention (21-day cycle)
1 Safety Run-in	A	Ad-RTS-hIL-12 monotherapy (n=6) [INXN-1001 (140 mg daily) + INXN-2001 [REDACTED] [REDACTED] [REDACTED]
	C	Combination therapy; n=3 [INXN-1001 (140 mg daily) + INXN-2001 [REDACTED] [REDACTED] [REDACTED] + palifosfamide (120 mg/m ²)]
2 Randomization	A	Ad-RTS-hIL-12 monotherapy [INXN-1001 (140 mg daily) + INXN-2001 [REDACTED] [REDACTED] [REDACTED]
	C	Combination therapy [INXN-1001 (140 mg daily) + INXN-2001 [REDACTED] [REDACTED] [REDACTED] + palifosfamide (120 mg/m ²)]

5. SUBJECT SELECTION

The target population for this study is adult subjects with recurrent and/or metastatic adenocarcinoma of the breast with accessible tumors (eg, in the opinion of the investigator is/are palpable and/or injectable) not amenable to surgical resection or radiation with curative intent.

5.1 Inclusion Criteria

To be enrolled in the trial, each subject must satisfy all of the following inclusion criteria:

1. Males or females of all races \geq 18 years of age, who have provided written informed consent prior to completing any study-specific procedure.
2. Histologically or cytologically confirmed adenocarcinoma of the breast, either locally recurrent or metastatic disease with injectable lesions, for which no proven curative therapy exists. Locally recurrent disease must not be amenable to surgical resection or radiation with curative intent.
3. Subject has failed or progressed on at least 1 prior systemic chemotherapy regimen \pm biologic/experimental therapy (if first-line therapy, failure or progression during or within the first 30 days).
4. Resolution of all chemotherapy or radiation-related toxicities to Grade 1 severity or lower, except for stable sensory neuropathy \leq Grade 2 and alopecia.
5. A minimum of 2 lesion(s) assessed by imaging using mRECIST v1.1. 1 or more lesions NOT to be injected AND at least 1 injectable lesion(s) (eg, may use radiographically-guided injection of lesions if available at site)
6. Eastern Cooperative Oncology Group (ECOG) performance status 0, 1, 2
7. Male and female subjects must agree to use a highly reliable method of birth control (expected failure rate less than 5% per year) from the screening visit through 28 days after the last dose of study drug. Women of childbearing potential (perimenopausal

women must be amenorrheic for at least 12 months to be considered of non-childbearing potential) must have a negative pregnancy test at screening.

8. Adequate bone marrow reserve as indicated by:
 - a) Absolute neutrophil count (ANC) $> 1500/\mu\text{L}$ (without use of growth factors within 7 days)
 - b) Absolute lymphocyte count (ALC) $> 700/\mu\text{L}$ (without use of growth factors within 7 days)
 - c) Platelet count $> 100,000/\text{mm}^3$ (without transfusion in prior 7 days)
 - d) Hemoglobin $> 9.0 \text{ g/dL}$ (without transfusion in prior 7 days)
9. Adequate renal function as evidenced by eGFR using the Modification of Diet in Renal Disease (MDRD) equation: $\text{eGFR} \geq 60 \text{ mL/min}/1.73 \text{ m}^2$
10. Adequate liver function as evidenced by the following:
 - a) Bilirubin ≤ 1.5 times the upper limits of normal (ULN)
 - b) ALT and AST $\leq 2.5 \times \text{ULN}$, in the case of liver metastases $\leq 5 \times \text{ULN}$

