14. Centralized registration of eligible subjects will be completed according to a process defined by the Sponsor. During Part 1 of the study, subjects will be registered by the Medical Monitor to one of the treatment arms; during Part 2, subjects will be randomly assigned to a treatment arm.
15. Appropriate cancer staging procedures should be performed during screening. For the purpose of this clinical trial, the following imaging is expected at screening:
 - a. CT of the chest, and CT (or MRI) of the abdomen
 - b. MRI (or CT) of the brain, if brain metastasis are known or suspected
 - c. CT or MRI of other anatomical regions as clinically indicated

All imaging should be of diagnostic quality and include IV contrast. PET imaging is an acceptable alternative modality provided the CT component is of diagnostic quality as per RECIST 1.1 guidelines.

For subjects with measurable lesions, target lesions should be selected and measured as per mRECIST v1.1 guidelines. ([Appendix 4](#)) Lesions that will be/are injected with INXN-2001 and/or biopsied should not be selected as target lesions, but should be assessed qualitatively as non-target lesions.

Disease sites are to be imaged throughout the study using the same method(s) used at screening. Chest and abdomen imaging are required for all follow-up imaging time points; images of the brain and other anatomical regions should be acquired on follow-up if positive at screening and as clinically indicated.

Tumor response assessments will occur at 12 weeks and 16 weeks (C5D1 and C6D7), and the Follow-up Tumor Assessment visit (24 weeks) for all subjects, including those who may have experienced a dose delay. In the setting of this immunotherapy, a progression observed at week 12 requires confirmation at week 16. Additional tumor response assessments may occur at the discretion of the investigator.

16. A blood sample(s) for cytokine profiling, breast cancer-associated biomarker levels (eg, MUC-1), and also INXN-1001 levels. Please refer to the Laboratory Manual for details regarding sample processing and shipment.

Screening (post-registration)

Cycle 1 - Days 2, 3, 7, and 15

Cycle 3 - Days 2, 3, 7, and 15

[figure not shown]
Cycle 5 - Day 1 (to coincide with the tumor assessment)

Cycle 6 - Days 2, 3, 7, and 15

Post-treatment Safety Assessment

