13.4 Appendix 4: Modified RECIST Criteria

Progression-free survival (PFS) rate and response to treatment will be determined on the basis of RECIST v.1.1³⁵ as applied to this trial, taking into account response patterns that have been observed with immunotherapies. In studies with a diversity of immunotherapies in different cancer types, objective responses have been shown to occur after an initial increase in tumor burden characterized as PD by World Health Organization or RECIST criteria.³⁶

The 4 observed patterns of response to immunotherapy in subjects with advanced cancer have been:

1. Immediate response - response in baseline lesions-evident by week 12, with no new lesions
2. Durable stable disease - which in some subjects was followed by a slow, steady decline in total tumor burden
3. Response after initial increase in tumor burden
4. Response in the presence of new lesions - a reduction in total tumor burden during or after the appearance of new lesion(s) at time points later than week 12

To capture these response patterns observed with some immunotherapeutic agents, a modification of RECIST v1.1 (mRECIST) will be utilized.

At Baseline:

The disease burden at baseline will be categorized into target and non-target lesions.

A maximum of 5 target lesions (no more than 2 target lesions per organ), representative of all involved organs, may be selected.

Target lesions are lesions that can be accurately measured in at least one dimension and whose minimum lesion size is as follows:

- Non-nodal lesions ≥ 10 mm or ≥ 2 times the slice thickness/reconstruction interval
- Nodal target lesions (lymph nodes): the short axis must measure ≥ 15 mm irrespective of modality/scanner type and slice thickness/interval

Lesions that are/will be injected with INXN-2001 and/or biopsied should not be selected as target lesions.

At Each Subsequent Assessment:

Target lesions are measured at every time point and an overall Sum of Diameters (SOD) will be determined by adding the longest diameters of all non-nodal lesions and short axes (ie, widest dimensions perpendicular to the long axes) of nodal lesions.

Target lesions are assessed as Complete Response (CR), Partial Response (PR), Stable Disease (SD), Progressive Disease (PD), or Not Evaluable (NE) at every time point based on the SOD.

Target Lesion Assessment	Definition

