Complete Response (CR)	CR is declared if all of the following are true for target lesions: 
• The disappearance of all non-nodal target lesions• Any pathological lymph nodes must have a reduction in short axis to <10 mm.
Partial Response (PR)	PR is declared if there is a decrease of at least 30% in the sum of diameters of target lesions taking as reference the baseline sum of diameters of target lesions.
Progressive Disease (PD)	PD is only declared if all of the following are true for target lesions: 
• SOD of all target lesions increases at least 20% taking as reference the smallest SOD recorded at or after baseline• Actual SOD increase is ≥ 5 mm from the smallest SOD recorded at or after baseline
Stable Disease (SD)	SD is declared if target lesion assessment does not meet criteria for PR, PD or CR

Selection and Assessment of Non-Target Lesions:

Non-target lesions are all other lesions, including additional potentially measurable lesions and truly non-measurable lesions, such as lesions that are/will be injected with INXN-2001 and/or biopsied, all bone lesions, ascites, pleural and pericardial effusion, inflammatory breast disease, lymphangitic involvement of skin or lung, and brain lesions. Non-target lesions will be assessed qualitatively, and the possible assessments are CR, Non-CR/Non-PD (NN), and PD.

If pleural effusions or ascites (selected as non-target lesions at baseline) are stable in size or minimally enlarging, they will be assessed as NN. New fluid collections or any effusion that significantly worsens will be considered a sign of PD unless cytopathology results are available that support a non-malignant nature.

Non-target lesions should only be assessed as PD if the progression is unequivocal. In the setting of a subject who also has measurable disease, there must be an overall level of substantial worsening in the context of the overall disease burden. A modest increase in size of one or more non-target lesions is not considered sufficient to qualify for unequivocal progression status. In the absence of measurable disease, the change in the overall non-measurable disease burden should be comparable to at least a 20% increase in overall diameter or 73% in approximate overall volume.

New Lesions:

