The determination of new lesions should be unequivocal and not be attributable to differences in the scanning technique, change in modality, or findings thought to represent something other than tumor. This is particularly important when the subject's baseline lesions show PR or CR.

New lesions should be reported as equivocal or unequivocal when first noted. New lesions observed at week 12 should not be considered as unequivocally progression; however, they should be re-assessed at subsequent time points. Lesions that were noted as equivocal should be re-assessed as Equivocal, Unequivocal, NN, PD, or Benign on subsequent time points. Lesions that were unequivocal should be re-assessed as Unequivocal, Absent, or NE.

As initial flare-ups have been reported in the context of immunotherapy, new lesions should only be taken as a sign of progression if they are:

- Unequivocally present, and
- Defined as clinically significant.

Clinical significance should relate to the size and location of the new lesion, such as new brain involvement, significant vascular invasion or compression.

Any lesion that does not meet the above criteria should be considered an equivocal new lesion that does not justify in isolation an overall assessment of progression at that time point. Such equivocal new lesions should be re-evaluated at the next time point.

Overall Response Assessments:

Target Lesions	Non-Target Lesions	New Lesions	Time Point Response
CR	CR	No	CR
CR	NN or NE	No	PR
PR	Non-PD (including NE)	No	PR
SD	Non-PD (including NE)	No	SD
PD	ANY	Yes/No	PD^a
ANY	PD	Yes/No	PD^a
ANY	ANY	Yes	PD^a
NE	Non-PD	No	NE

^a PD at \leq week 12 requires confirmation at week 16.

NN = Non-CR/Non-PD

NE = Not Evaluable

13.5 Appendix 5: Modification of Diet in Renal Disease (MDRD) Equation for Estimating Glomerular Filtration Rate (eGFR)

The eGFR adjusted for body surface area will be calculated using serum creatinine (SCr) and the 4-variable MDRD equation.³⁸

When using isotope dilution mass spectrometry (IDMS)-traceable serum creatinine:

- For creatinine in mg/dL:

$$\text{eGFR (mL/min/1.73 m}^2\text{)} = 175 \times (\text{SCr})^{-1.154} \times (\text{Age})^{-0.203} \times 0.742 \text{ (if female)} \times 1.212 \text{ (if Black)}$$

- For creatinine in $\mu\text{mol/L}$:

$$\text{eGFR (mL/min/1.73 m}^2\text{)} = 30,849 \times (\text{SCr})^{-1.154} \times (\text{Age})^{-0.203} \times 0.742 \text{ (if female)} \times 1.212 \text{ (if Black)}$$

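### Subjects with no target lesion are eligible and can be scored as progressing, but the overall-response table gives them no row for stable disease or complete response, so CBR depends on how sites code them and ORR includes subjects who cannot have a PR.

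*Protocol*

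**What the plan says.** **Eligibility.** Inclusion criterion 5 (synopsis and Protocol 5.1) requires "A minimum of 2 lesion(s) assessed by imaging using mRECIST v1.1", with at least one lesion left un-injected and at least one injectable. Measurability is not mentioned.

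**Target lesions.** Appendix 4 states: "Lesions that are/will be injected with INXN-2001 and/or biopsied should not be selected as target lesions". Footnote 15 to Tables 2A and 2B makes target selection conditional: "For subjects with measurable lesions, target lesions should be selected and measured as per mRECIST v1.1 guidelines". Target lesions are graded CR, PR, SD, PD "or Not Evaluable (NE) at every time point based on the SOD", that is, on the sum of diameters.

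**No measurable disease.** Appendix 4 gives this case a progression threshold: "In the absence of measurable disease, the change in the overall non-measurable disease burden should be comparable to at least a 20% increase". It gives no matching rule for stability or response.

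**The table.** Under "Overall Response Assessments", every non-PD row starts from a target-lesion result of CR, PR, SD or NE. PD can be reached whatever the target result.

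**Endpoints.** Protocol 8.4.2 defines CBR as the proportion with CR, PR or SD, and ORR as the proportion with confirmed CR or PR. Both are analysed in the Efficacy Evaluable Population (8.3, 8.6.4), which needs one dose and one post-screening response evaluation but not measurable disease.

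**The concern.** The rules are one-sided for a group that the protocol itself expects. A subject with one injectable lesion and otherwise only bone disease, an effusion, lymphangitic disease or nodules below target size meets criterion 5 and has no target lesion. That subject can be scored as PD, but no row leads explicitly to SD or CR.

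Two secondary endpoints are exposed. CBR loses stable subjects if they are recorded as NE, and it can vary with the coding habits of about 30 planned centers in an open-label trial. ORR is taken over all subjects, some of whom cannot have a PR. The synopsis says that futility decisions draw on secondary as well as primary endpoints, so arm expansion could be touched, although no ORR or CBR threshold is given.

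**Working it through.** **The plan's own figures.** None bears directly on this point. The Simon designs in Protocol 8.1 reproduce as two-stage exact binomial calculations:
- Arm A (at least 3 of 13, then at least 9 of 33; 15% against 35%, leaving aside the synopsis's six-subject look): type I error 0.041, power 0.808.
- Arm C (at least 6 of 12, then at least 15 of 26; 40% against 65%): type I error 0.047, power 0.809.

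Both agree with the stated one-sided 5% and 80%. They use only the 16-week PFS rate, so the SD-or-NE label does not enter them.

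**Walking a no-target subject through the Appendix 4 table.**

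| State of disease | Row available | Result |
|---|---|---|
| Non-target PD, or qualifying new lesion | Target ANY | PD |
| Non-target Non-CR/Non-PD, no new lesion | Closest fit: target NE with Non-PD | NE |
| All non-target disease gone, no new lesion | CR row needs a target CR | No explicit row |

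NE is the closest fit because target categories rest on the sum of diameters, and this subject has none. PR at target level is a fall in that sum. The other route to an overall PR needs a target CR, which would have to be declared on an empty set of lesions.

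**Size for CBR.** Inputs:
- f, the share with no target lesion: not in the documents; assumed 10% to 30%.
- c, the true CBR: assumed 65% in both groups, as an illustration only.
- n = 26, Arm C: 12 + 14 (Protocol 8.1).

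If no-target subjects are all recorded as NE and stay in the denominator, reported CBR = c × (1 − f):
- f = 10%: 0.65 × 0.90 = 58.5%
- f = 30%: 0.65 × 0.70 = 45.5%

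The loss is c × f, or 6.5 to 19.5 points. In subjects, that is 26 × 0.065 = 1.7 to 26 × 0.195 = 5.1.

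With c = 50%:
- Arm C with 3, 5 or 8 no-target subjects of 26: 44.2%, 40.4%, 34.6%.
- Arm A with 3, 7 or 10 of 33: 45.5%, 39.4%, 34.8%.

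**The other possible codings.** If sites enter SD, reported CBR equals c and nothing is lost. If an NE-only subject is held to have no response evaluation, that subject leaves numerator and denominator. CBR is then still c under the equal-rate assumption, but on 23 to 18 subjects (26 − 3 to 26 − 8).

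**Size for ORR.** Assume an ORR of 20% among subjects with a target lesion and no CR among those without. The all-subjects ORR is 0.20 × (1 − f):
- Arm C with 3, 5 or 8 of 26: 17.7%, 16.2%, 13.8%.
- Arm A with 3, 7 or 10 of 33: 18.2%, 15.8%, 13.9%.

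**The case against.** The best reply is that no rule sends these subjects to NE. Appendix 4 defines SD as the category left when PR, PD and CR are not met, so a site could enter SD, and the table would return SD. A reader might infer a systematic loss from CBR, but the documents do not establish one. What they establish is a missing rule whose most natural reading gives NE. That part of the reply stands, and it also shows that two sites could code the same subject differently.

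Further points:
- Appendix 4 is built on RECIST v1.1 and does not say whether cases it omits revert to the parent criteria. The appendix is taken here as the operative text.
- Protocol 6.2.4.3 narrows the group: without radiographically guided injection, one accessible lesion stays un-injected. Accessible does not mean measurable, however, and sites with guidance remain open. In the other direction, Appendix 6 sites biopsy non-injected tumor or draining nodes, which bars those lesions as targets.
- An all-subjects ORR is a legitimate, conservative definition. A reader might call it an error; the documents do not support that. The case is for a supplementary figure.
- The SAP does not settle the matter. It describes a single-arm, single-center, one-cycle study with 12-week endpoints. Its own response table lacks the row too, and it counts subjects who cannot be assessed as non-responders.

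**Conclusion.** The gap is real and worth closing, as a point about secondary endpoints. Eligibility admits subjects with no permitted target lesion, Appendix 4 anticipates subjects without measurable disease, and the table gives them no explicit route to SD or CR. CBR is understated only if two things hold: NE is recorded, and the subject counts as having a post-screening response evaluation, which Protocol 8.3 leaves open. On the assumed 10% to 30% share and 65% true CBR, the loss is 6.5 to 19.5 points, about 2 to 5 of 26 subjects.

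Three stronger readings should be resisted:
- The 65% is not a CBR target. The protocol's 65% for Arm C is the targeted proportion progression-free at week 16.
- The 3 to 8 of 26 subjects without target lesions (26 × 0.1 = 2.6 to 26 × 0.3 = 7.8) are not all lost from CBR. Only those with disease control are.
- The primary endpoint is not shown to be biased. Protocol 8.4.1 counts progression and death and asks for a tumor assessment reaching week 16; it does not use SD or NE. The open residue is whether a time point labelled NE counts as an assessment.

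**What to change.** Add rows to the Appendix 4 overall-response table for subjects with no target lesion at baseline:
- non-target CR, no new lesion: CR;
- Non-CR/Non-PD, no new lesion: Non-CR/Non-PD, treated as progression-free and as disease control for CBR;
- non-target PD or a qualifying new lesion: PD, subject to the existing week-16 confirmation rule.

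Keep the all-subjects ORR and report ORR also in subjects with at least one target lesion at baseline. Both parts are needed: the rows settle CBR, but they do not change the fact that these subjects cannot have a PR. Counting Non-CR/Non-PD as disease control is a choice, so it should be written down before the data are reviewed.

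The cost is table wording and one extra ORR summary. Eligibility, visits and procedures do not change.
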